RESEARCH PROTOCOL

Single lung ventilation refers to the situation in which one lung is ventilated and the other lung is deflated, mechanically separating the two lobes of the lung. Single lung ventilation is performed to facilitate surgical access in intrathoracic procedures involving the lung, esophagus, anterior mediastinal structures, and aorta, as well as in selected orthopedic spine procedures (1). There are three types of lung isolation methods; 1. Double-lumen endobronchial tube, 2. Broach blocker, 3. Single-lumen endobronchial tube (2). The most commonly used method for single-lung ventilation is intubation with a double-lumen endobronchial tube (3), (4). Double-lumen tubes allow isolation of both lungs, selective ventilation, and intermittent suctioning. A double-lumen tube has separate tracheal and bronchial lumens; it is essentially two tubes connected side by side. The shorter tube has a high-volume, low-pressure tracheal head and forms the tracheal lumen positioned just above the carina. In both left and right double-lumen tubes, the smaller, low-volume, high-pressure bronchial cuff is ideally positioned just below the tracheal carina and before the division of the lobar bronchus. The cuffs pilot balloons and the connection areas at the top of each of the two tubes are all color-coded (white for the tracheal tube and blue for the endobronchial tube). When the double-lumen tubes are properly positioned, both the tracheal and bronchial cuffs are inflated, clamping the lumen of the opposite lung to provide selective single-lung ventilation. Left double-lumen tubes are most often selected because of the longer left main bronchus, easier positioning, and greater margin of error compared to right double-lumen tubes. The length of the left bronchus is 4-6 cm in men and 3-5 cm in women, while the length of the right main bronchus is 1-2 cm. It is more difficult to maintain the position of right double-lumen tubes than left double-lumen tubes, therefore complications due to incorrect positioning may be more common. For these reasons, the use of right double-lumen tubes is limited to special situations. These are; left pneumonectomy, distorted anatomy of the left main bronchus entrance due to external and intraluminal compression, and the surgical site containing the left main bronchus. Placement of left double-lumen tubes is generally easier than right double-lumen tubes. Under direct laryngoscopy, the endobronchial tip is inserted between the vocal cords, the stylet is removed, and the double-lumen tube is rotated 90 degrees to the left while advancing. Airway damage (hoarseness, sore throat, tracheal rupture) and hypoxemia may occur due to incorrect positioning of the double-lumen tube (5). Traditionally, the position of the left double-lumen tube is confirmed by auscultation. Initial auscultation is performed with both tracheal and bronchial cuffs inflated; if the double-lumen tube is properly inserted, ventilation through both lumens should result in equal bilateral breath sounds. The tracheal lumen is then clamped and ventilation should result in breath sounds on the left side but not the right. The bronchial lumen is then clamped and ventilation should result in breath sounds on the right side but not the left. Fiberoptic bronchoscopy is the gold standard for confirming the position of double-lumen tubes (6). If the left double-lumen tube is ideally positioned, the initial bronchoscopic view through the tracheal lumen will show a blue bronchial balloon visible just beyond the carina on the left side without herniation into the trachea. The tube is then confirmed by advancing the bronchoscope into the bronchial lumen to ensure that the bronchial tube has not been advanced too far. The video double lumen tube, which has been used in recent years, is a technique where the tube location can be continuously seen on the screen during the application and surgery, but it has not become very widespread yet (7), (8). The primary purpose of this study is to investigate the superiority, advantages and disadvantages of these techniques used for the correct and short-term positioning of the double lumen tube in single lung ventilation. The secondary purpose is to determine the method that will ensure that the tube location can be verified in the shortest time and that intraoperative location changes can be detected in a short time, and that complications that may occur due to incorrect placement of the double lumen tube can be prevented, thus reducing complications. Other purposes are to perform the intubation procedure with the double lumen tube in the shortest time and verify its location in the shortest time, to save time, to prevent complications by detecting tube location changes in the intraoperative period in the shortest time, and thus to provide the shortest and safest operation time. Shortening the duration and preventing complications will also reduce costs. Although it has been stated in the literature that video double

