
RESEARCH PROTOCOL

lumen tubes are cost effective, their superiority over other techniques has not been demonstrated because their use has not yet become widespread. Another aim of the study is to compare the cost effects of these three methods.

Using the studies in the literature, the total number of patients for three groups was found to be 93 by using G-power to calculate the sample size and taking the effect size as 0.33 at a 95% confidence level and 80% power.

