In Kayseri City Hospital, ASA I-III patients aged 18-84 who are planned to undergo surgery with single lung ventilation between December 2024 and May 2025 will be included in the study after obtaining their informed consent. In our hospital, video double lumen tube verification techniques, and auscultation and fiberoptic bronchoscopy are routinely used for conventional double lumen tubes. Patients are blinded in terms of the method to be applied, and since the anesthesiologist who will perform the intubation procedure is the person who performs the method, blinding cannot be performed. Anesthesiologists who perform the intubation procedure will not have any information about the study. They will use the method they prefer. Patient randomization will be done in this way. In the study, volunteers were blinded because they did not know which intubation method would be used, while blinding could not be done for the anesthesiologist who would perform the intubation. Due to the advantages mentioned above, a left tube will be used in all patients. Tube sizes will be determined according to the height and gender of the patients. Group I will be divided into three groups randomly as patients whose tube location will be confirmed by auscultation, Group II patients whose tube location will be confirmed by using fiberoptic bronchoscopy, and Group III patients whose tube location will be confirmed by using a video-guided double-lumen intubation tube. After the patients are taken to the operating room, routine monitoring will be applied and vascular access will be established with an 18G intravenous catheter. After preoxygenation with 100% O₂ for 2 minutes, anesthesia induction will be applied with 2-3 mg/kg propofol, 1-2 mcg/kg fentanyl, and 0.6mg/kg rocuronium. They will be ventilated with 100% oxygen until neuromuscular blockade occurs for at least 2 minutes. The intubation duration will be started after the vocal cords are visualized with the laryngoscope and will be taken as the time until end tidal CO₂ is seen on the monitor. Intubation verification time was planned for Group I as the time when bilateral respiratory sounds are heard while both cuffs are inflated, then the tracheal lumen is clamped and no respiratory sounds are heard on the right, respiratory sounds are heard on the left and then the bronchial lumen is clamped and no respiratory sounds are heard in the left lung, and respiratory sounds are confirmed to be heard in the right lung. For Group II, it was planned to be taken as the time when the fiberoptic bronchoscope is first entered into the tracheal lumen and the carina and bronchial blue-colored cuff is seen to be inflated without herniation in the left bronchus and then entered through the left bronchial lumen and it is seen that the tube is not advanced too much. III. In the group, it was planned to be taken as the time when the bronchial lumen of the video double lumen tube entered the left bronchus and the blue cuff was inflated. After the patients were given the lateral decubitus position with the lung to be operated on top, the tube location for each group was confirmed again and the time was recorded. Anesthesia maintenance will be provided using 1 MAC sevoflurane. The number of intubation attempts in the 3 groups, the duration of intubation, the duration of tube location verification, the quality of lung collapse, the need for fiberoptic bronchoscopy, the duration of fiberoptic bronchoscopy, the number of tube dislocations, and the duration of dislocation correction will be monitored. After extubation, the patients will be taken to the recovery room. In the recovery room, the patients will be questioned about the presence of sore throat and hoarseness. The methods used in the patients will be compared in terms of cost according to the type of tube and the use of fiberoptic. The data to be collected for the study will be recorded using the SPSS 22 program and analyzed in the same program. Frequency, percentage, mean value, standard deviation, maximum and minimum (min-max) values will be used for descriptive statistics, Pearson Chi-square test will be applied for statistical analysis of categorical data and Fisher's Exact Test will be applied for values below five in four-sided tables.

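### Verification time has no stated start in any group, and Group III's stop may fall inside the intubation interval, so a difference could partly reflect the clocks

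*Protocol*

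**What the plan says.** All the timing rules are in the Protocol's methods paragraph.

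- **Intubation duration** has both ends. "The intubation duration will be started after the vocal cords are visualized with the laryngoscope", and it runs until end tidal CO2 appears on the monitor.
- **Verification time, Group I**, is the time when a sequence is met: bilateral sounds with both cuffs inflated, then each lumen clamped in turn, ending when "respiratory sounds are confirmed to be heard in the right lung".
- **Verification time, Group II**, is the time when "the fiberoptic bronchoscope is first entered into the tracheal lumen", the inflated cuff is seen in the left bronchus without herniation, and the scope is "then entered through the left bronchial lumen and it is seen that the tube is not advanced too much".
- **Verification time, Group III**, is "the time when the bronchial lumen of the video double lumen tube entered the left bronchus and the blue cuff was inflated".
- **After lateral positioning**, the location is confirmed again in each group and a time is recorded, with no further rule.

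The duration of verification is listed among the outcomes for the three groups, separately from intubation duration. The secondary purpose includes finding "the method that will ensure that the tube location can be verified in the shortest time". The SAP names tests for quantitative data (ANOVA or Kruskal-Wallis for three groups) but does not define this variable. The need for fiberoptic bronchoscopy and its duration are also listed as outcomes, without saying whether Group II's own verification bronchoscopy counts.

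**The concern.** A duration needs a start and a stop, and a comparison of durations needs them to mean the same thing in each group. Here the start is unstated, and the stops are not clearly equivalent. The video tube can be checked while it is being placed, which may be a real benefit. The definitions cannot separate that benefit from time that has only moved from the verification interval to the intubation interval. What is at stake is the answer to a stated purpose: an observed difference, or the absence of one, could be partly a product of the definitions. A time stamp not taken during the case cannot be recovered at analysis.

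**Working it through.** **1. The clocks side by side (Protocol, methods paragraph).**

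| Clock | Stated start | First step named | Last event named |
|---|---|---|---|
| Intubation, all groups | vocal cords visualised | not needed | end tidal CO2 seen |
| Verification, Group I | none | bilateral sounds, both cuffs inflated | right-sided sounds confirmed |
| Verification, Group II | none | scope enters tracheal lumen | depth seen to be acceptable |
| Verification, Group III | none | none | bronchial lumen in left bronchus, cuff inflated |
| Lateral re-check, all groups | none | none | none |

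The cuff inflation that closes Group III's clock precedes the first step named for Group I. The Protocol does not say whether Group III's closing event comes before or after end tidal CO2 is seen.

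**2. The direction depends on the missing start.**

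- Start at vocal cords: verification time in every group contains placement time and overlaps intubation duration.
- Start at end tidal CO2: if Group III's event has already happened, its time is zero or negative.
- Start at the first step of each check: Groups I and II begin at different events, and Group III has none. If its clock then began at laryngoscopy, its time would contain placement that the other two exclude.

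So Group III could look faster or slower with no change in what was done.

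**3. The plan's own figure.** The sample size comes from "taking the effect size as 0.33 at a 95% confidence level and 80% power". Reading 0.33 as Cohen's f (the metric is not named), with three groups, alpha 0.05 and noncentrality λ = N × f² = 93 × 0.1089 = 10.13, power at N = 93 is 0.807. At N = 90 it is 0.793. With equal groups of 31 the total of 93 reproduces. The Protocol does not tie this figure to verification time, so the point does not affect N.

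**4. Illustration only.** The documents give no times, SDs or offsets. Assume equal true times, otherwise comparable groups, normal data, and a purely definitional shift of d SD in Group III. With n₃ patients in Group III and the rest split equally, λ = d² × n₃(93 − n₃)/93. For n₃ = 31, λ = 20.67d², which is 1.29, 5.17 and 10.13 at d = 0.25, 0.5 and 0.7. ANOVA rejection at a nominal 5%:

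| Group III size | d = 0.25 | d = 0.5 | d = 0.7 |
|---|---|---|---|
| 31 of 93 | 16% | 50% | 81% |
| 15 of 93 | 11% | 33% | 58% |
| 46 of 93 | 17% | 56% | 85% |

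The 81% equals the design power by construction, because d = 0.7 with equal groups is f = 0.7 × √2/3 = 0.33. In the opposite direction, with 31 per group, a true saving of 0.7 SD offset by 0.25 or 0.5 SD of placement time leaves a net 0.45 or 0.20 SD. Power falls from 81% to 42% or 12%.

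**5. Bronchoscopy need, if Group II's own check counts.** Take 31 of 31 in Group II and assume r of 31 in each of Groups I and III. For r = 25 the expected counts are 27 yes and 4 no per group. Then χ² = (4 + 16 + 4)/27 + (4 + 16 + 4)/4 = 6.89 on 2 df, p = 0.032. For r = 15, χ² = 24.39, p = 5 × 10⁻⁶; for r = 26, χ² = 5.60, p = 0.061. Groups I and III are identical in every case, so any significance comes from the group label.

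**The case against.** **Group III is confirmed too.** A reader might infer that Group III's clock stops with no confirmation at all. The documents do not support that. The methods paragraph defines Group III as patients whose tube location is confirmed with the video tube, and it says location is confirmed *again* in each group after positioning. The background says "the tube location can be continuously seen on the screen during the application and surgery". The natural reading is that entry and inflation are seen on the screen. This stands. It leaves two gaps: Group III's criterion omits Group II's herniation and depth items, and its place relative to end tidal CO2 is open.

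**Starts can be inferred.** Groups I and II are both worded as a first step followed by later steps, so both can be read as first-to-last-step durations. A start at the end of intubation is also plausible, because the two durations are listed separately. That is fair. But the two readings give different clocks, and the first gives Group III no start.

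**Different checks are inherent to comparing methods.** True, and no one needs to make the checks alike. A common start and a common declared stop leave each method's check as it is.

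**The percentages prove little.** Also true. They show only that an assumed shift is detected as a shift. They further assume comparable groups, although anesthesiologists use the method they prefer. Nor does the plan name a test for bronchoscopy need, and need may mean bronchoscopy beyond the group's own method, in which case that point falls away.

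**Conclusion.** The point holds in this form. Verification time has no stated start in any group, the first steps named for Groups I and II differ, and Group III's stop is a placement event that may fall inside the intubation interval. A difference in verification time could partly reflect these definitions. The direction is unknown and the size cannot be computed from the documents.

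A reader might go further and conclude that the three times cannot be compared at all, or that the false-positive rate is some figure in the table above. Neither follows: site practice may use a consistent clock that the Protocol does not state, and every offset shown is assumed. Outcomes that do not use this clock are unaffected by the timing defect. The plan should be corrected because a stated purpose depends on it and the remedy is small. The bronchoscopy point is separate and conditional on how need is counted.

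**What to change.** 1. **One start and one stop for verification time in all groups.** Start at end tidal CO2 seen, which already ends intubation duration. Stop when the operator declares the position confirmed by the method in use. Write down each method's criteria; add no checks.
2. **Report total time** from vocal cords visualised to confirmation beside intubation and verification times, as a supporting comparison. Rely on it where confirmation precedes end tidal CO2, since it does not depend on where placement ends and checking begins.
3. **Lateral re-check:** the same stop, with one stated start such as completion of positioning.
4. **Cases already recorded:** state the start and stop actually used and report the comparison descriptively.
5. **Bronchoscopy:** compare need and duration beyond the group's own method between Groups I and III, and report Group II descriptively.

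**Cost.** One extra time stamp, with no change to N. The result is time to declared confirmation, not time to proven correct position.

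A reader might want total time as the main comparison, but it is noisier. For a true saving of 0.7 verification SD, the standardised effect on the total is 0.7/√(1 + s² + 2ρs), where s is the ratio of intubation SD to verification SD and ρ their correlation. With 31 per group:

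| s | ρ | Effect | Power |
|---|---|---|---|
| 0.5 | 0 | 0.626 | 71% |
| 1 | 0 | 0.495 | 49% |
| 1 | 0.5 | 0.404 | 35% |

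A well-defined verification interval has 81%. These SD ratios and correlations are assumed. They are the reason to keep the total as support.

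### Intubation duration differs by method only in Group III, but the plan names no conventional-tube (Groups I and II) versus video-tube contrast for it

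*Protocol*

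**What the plan says.** All of the design detail is in the Protocol's methods paragraph.

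- **Groups.** They are defined by how tube position is confirmed: auscultation (I), bronchoscopy (II: "Group II patients whose tube location will be confirmed by using fiberoptic bronchoscopy") or the video tube (III). At this hospital "auscultation and fiberoptic bronchoscopy are routinely used for conventional double lumen tubes". Every patient gets a left-sided tube, sized by height and gender, and one induction regimen is described for all.
- **Intubation clock.** There is one definition for all groups. Timing starts when the vocal cords are seen and "will be taken as the time until end tidal" CO2 appears on the monitor. Verification time is defined separately, with its own criteria for each group.
- **Outcomes.** "The number of intubation attempts in the 3 groups, the duration of intubation, the duration of tube location verification" head a list of items to be monitored. An attempt is not defined.
- **Allocation.** Of the anesthesiologists the Protocol says "They will use the method they prefer".
- **Tests.** The Protocol's statistical paragraph and the SAP list the unpaired t test, one-way ANOVA with Tukey, Mann-Whitney U and Kruskal-Wallis. Neither assigns a test to an outcome or names a contrast that combines Groups I and II.
- **Sample size.** "the total number of patients for three groups was found to be 93 by using G-power", "taking the effect size as 0.33 at a 95% confidence level and 80% power". The outcome behind the effect size is not stated.

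**The concern.** Auscultation and bronchoscopy, as described, are checks on a tube already in place: one needs ventilation through a cuffed tube, the other looks for the inflated bronchial cuff. Nothing in the text separates Group I from Group II while the intubation clock runs. A Group I versus II difference in intubation duration could therefore come from the operator, the patient or chance, but not from the verification method.

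Two things follow if the outcome is analysed with the listed three-group tests. First, the output includes a Group I versus II comparison that is easily misread as a method effect. Because the operator chooses the method, a difference through operator or case mix is quite possible. Second, dividing the conventional-tube patients in two spends power on a contrast with no method content. Intubating in the shortest time is one of the Protocol's stated other purposes, so the outcome is likely to be reported.

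**Working it through.** **Inputs from the Protocol:** effect size 0.33, read as Cohen's f; 95% confidence, so alpha 0.05; power 80%; 93 patients in three groups.

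**Assumptions:** two-sided pairwise tests, normal data, a common SD, no dropout, Groups I and II with equal means, and Group III differing by d SDs. Equal groups (31 each) first, then other splits.

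**1. The plan's own figure.** For a one-way ANOVA the noncentrality is N × f², with 2 and N − 3 df. At N = 93 it is 93 × 0.33² = 10.13, and power is 80.7%. The smallest N reaching 80% is 92, or 93 as a multiple of three. The stated 93 is reproduced.

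**2. What f = 0.33 means if only Group III differs.** With means (0, 0, d), f = d√2/3, so d = 0.33 × 3/√2 = 0.70 SD.

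**3. Power at 0.7 SD, 31 per group.**

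- Three-group F test: 80.7%, as in step 1.
- Groups I and II together (62) versus Group III (31), t test on 91 df: noncentrality 0.7 × √(62 × 31/93) = 3.18, power 88.3%.
- One Tukey pair (III versus I, or III versus II): noncentrality 0.7 × √15.5 = 2.76, critical value 2.383, power 64.6%. In 100,000 simulated trials at least one of the two pairs was significant in 79.9%, and both in 49.5%.

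The like-for-like loss is 88.3 − 80.7 = 7.6 points. The Tukey figure is for one multiplicity-adjusted pair and should not be the headline. For 80% power the combined contrast needs 75 patients in total.

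**4. Other differences, 31 per group.**

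| d (SD) | F test | I and II v III | One Tukey pair |
|---|---|---|---|
| 0.5 | 50.3% | 61.4% | 34.4% |
| 0.6 | 66.8% | 77.0% | 49.4% |
| 0.7 | 80.7% | 88.3% | 64.6% |
| 0.8 | 90.3% | 94.9% | 77.7% |
| 1.0 | 98.5% | 99.4% | 93.8% |

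**5. Unequal groups at 0.7 SD** (splits assumed, because allocation follows preference).

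| I/II/III | F test | I and II v III |
|---|---|---|
| 40/40/13 | 52.9% | 63.9% |
| 50/23/20 | 68.4% | 78.4% |
| 25/25/43 | 85.1% | 91.5% |

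The combined contrast has more power in every split tried. The size of Group III matters more than the choice of contrast.

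**6. The Group I versus II comparison.** If the two are truly equal, a false Tukey finding occurs in about 2% of simulated trials, and a false unadjusted t test in about 5%. As a comparability check, an unadjusted t test of 31 versus 31 has noncentrality 0.5 × √15.5 = 1.97 at 0.5 SD, and about 49% power.

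**The case against.** **Attempts.** An attempt is undefined. If re-intubation after failed verification counts as one, Groups I and II can differ by method, because the two checks may detect misplacement at different rates. Combining them would then hide a real effect. This stands. It is tempting to treat attempts exactly like duration, but the Protocol gives the end-tidal CO2 endpoint only for duration.

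**No test is stated.** The outcome list says what is monitored, not how it is compared. Two-sample tests are among those listed, so a conventional-versus-video comparison is unspecified, not excluded. This stands too. A reader might infer that the plan commits to reporting a Group I versus II difference as a method effect; the documents do not say so.

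**Size.** The effect size 0.33 is not tied to intubation duration, the figures assume normal data, and they do not carry over to a small count such as attempts. Equal groups are not to be expected under preference allocation. All of this stands, and the results are therefore conditional.

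**Confounding is the larger problem.** Combining Groups I and II leaves preference allocation in place, and the comparator becomes a mix of operators with different preferences. That is true, but it does not defeat the point: the three-group analysis has the same confounding, and the Group I versus II check costs nothing. With about 49% power at 0.5 SD, however, a null result there is weak reassurance.

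**Conclusion.** The point holds for intubation duration. On the procedure described, Group III alone differs by method up to end-tidal CO2, and the plan does not name the contrast that matches this. At 0.7 SD, a difference the documents do not tie to this outcome, the three-group F test gives up about 8 points of power with equal groups. In the unequal splits tried the loss is about 6 to 11 points. These figures rest on normal data, a common SD and equal means in Groups I and II.

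Two stronger readings are not supported. The planned tests do not have the wrong type I error; the issue is efficiency and misattribution. Nor does the argument reach verification time, dislocations or need for bronchoscopy, where Groups I and II do differ by method. Since the outcome belongs to the Protocol's other purposes, and not to its primary or secondary purpose, severity is minor.

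**What to change.** In the Protocol's statistical paragraph and the SAP:

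1. For intubation duration, prespecify Groups I and II together (conventional tube) versus Group III (video tube).
2. Report Group I versus II on this outcome descriptively, as a comparability check. State that a difference points to operator or case mix, which may also affect the verification-time results, and that no difference does not establish comparability.
3. Define an intubation attempt. If it ends at end-tidal CO2, use the same contrast for number of attempts; otherwise keep three groups for attempts.
4. Keep the three-group comparison for verification and later outcomes.

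The cost is wording only, with no new data or patients. The trial gives up a separate Group I versus II method claim on intubation duration, which the described procedure could not support. Confounding from operator preference remains and needs its own remedy.

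### Intubation, verification and bronchoscopy times are compared separately with no common elapsed time, so a method can look faster on verification without giving a verified tube sooner

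*Protocol*

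**What the plan says.** The protocol's methods paragraph lists its time outcomes as separate items: "the duration of intubation, the duration of tube location verification, the quality of lung collapse, the need for fiberoptic bronchoscopy", followed by "the duration of fiberoptic bronchoscopy, the number of tube dislocations, and the duration of dislocation correction will be monitored".

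The clocks are defined as follows.

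- **Intubation, all groups:** "The intubation duration will be started after the vocal cords are visualized with the laryngoscope and will be taken as the time until end tidal" (the sentence closes with carbon dioxide appearing on the monitor).
- **Verification, Group I:** "Intubation verification time was planned for Group I as the time when bilateral respiratory sounds are heard while both cuffs are inflated", continuing through the two clamping steps until the expected sounds are confirmed.
- **Verification, Group II:** "it was planned to be taken as the time when the fiberoptic bronchoscope is first entered into the tracheal lumen", ending after inspection through the bronchial lumen.
- **Verification, Group III:** "the time when the bronchial lumen of the video double lumen tube entered the left bronchus and the blue cuff was inflated".

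No start point is given for verification in any group. Verification is repeated and timed after lateral positioning.

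On aims, the protocol's secondary purpose is "to determine the method that will ensure that the tube location can be verified in the shortest time". A further purpose is "to perform the intubation procedure with the double lumen tube in the shortest time and verify its location in the shortest time", with the object of saving time.

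The SAP gives generic tests for quantitative variables (one-way ANOVA with Tukey, or Kruskal-Wallis, at p<0.05). It names no total time and no order among the outcomes.

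**The concern.** The three verification endpoints do not cut the work at the same place. In Groups I and II the endpoint is a check made on a tube that is already in. In Group III it is entry into the left bronchus with the cuff inflated, which is part of insertion. The protocol's introduction says the video tube's location is visible on screen during placement. That endpoint can therefore fall close to, or inside, the interval that the intubation clock measures.

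The plan also foresees bronchoscopy outside Group II, since the need for it is an outcome in all three groups. It does not say whether verification time keeps running when auscultation or the video view fails and a bronchoscope is used.

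At stake is the practical question: which method gives the quickest correctly positioned tube? The trial could report a shorter verification time for a method whose patients wait just as long for a confirmed tube. Separate group means would not let a reader rebuild each patient's total or its variance.

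**Working it through.** **1. The plan's own figure.** Inputs from the protocol's sample-size paragraph: total 93, three groups, effect size 0.33 (read as Cohen's f), 80% power, and 95% confidence (alpha 0.05). In a one-way ANOVA with noncentrality f²N, power is 79.7% at N=91, 80.2% at N=92 and 80.7% at N=93. The minimum is 92, or 93 with equal groups, so the stated number reproduces. The documents do not say which outcome the 0.33 refers to.

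**2. Time moving between clocks (assumed figures).** Take 31 per group (93/3; the allocation ratio is not stated) and normal data. Suppose Group III takes d SDs longer on intubation and d SDs less on verification, so its mean total is unchanged. With one group of three shifted, f = d√2/3.

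For example, a 20 s shift with SD 25 s gives d = 20/25 = 0.8. Then f = 0.8 × 1.414/3 = 0.377 and noncentrality = 0.377² × 93 = 13.2. ANOVA power on either clock is 90%. A single Tukey pairwise comparison has about 78%, and an unadjusted two-sample t test has 87%.

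Simulation (4,000 trials per row, SD 1 on each clock, clocks independent):

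| Shift (SD) | Intubation significant | Verification significant | Total significant |
|---|---|---|---|
| 0.5 | 51% | 50% | 5% |
| 0.8 | 90% | 89% | 5% |
| 1.0 | 98% | 99% | 5% |

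The total stays at the null rate because its mean does not differ between groups.

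**3. Rescue bronchoscopy (assumed figures).** This step applies only if the verification clock stops when rescue begins, which the documents leave open. Time outside the clock per patient = rescue rate × rescue duration; for example, 0.30 × 120 s = 36 s. An apparent advantage of G seconds is cancelled at a rescue rate of G divided by the rescue duration:

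| Advantage | 60 s rescue | 120 s rescue | 180 s rescue |
|---|---|---|---|
| 30 s | 50% | 25% | 17% |
| 60 s | 100% | 50% | 33% |

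**4. Power for a total.** Suppose f=0.33 belongs to one clock and the groups differ only on that clock. Let s be the other clock's SD as a multiple of this one's, and ρ their correlation. Then f for the total = 0.33/√(1 + s² + 2ρs).

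| s | ρ | f for total | Power at N=93 | N for 80% |
|---|---|---|---|---|
| 0.5 | 0 | 0.295 | 71% | 114 |
| 1 | 0 | 0.233 | 50% | 180 |
| 1 | 0.5 | 0.191 | 35% | 269 |

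If the other clock were twice as variable (s=2), power would fall further, to 22% at ρ=0 and 17% at ρ=0.5. If the groups differ in the same direction on both clocks, the loss is smaller or absent.

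**The case against.** The strongest reply is that the component outcomes answer the stated aims directly. The secondary purpose is about verification time, and the further purpose names intubation and verification separately. A method that gains on one clock and loses on the other would show both results side by side. Rescue is not hidden either: the need for bronchoscopy, its duration, dislocations and correction time are all recorded, and bronchoscope use enters the cost comparison. This stands as a reason to keep testing the components. It does not supply a like-for-like total.

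Three stronger readings are tempting, and the documents do not support them.

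- **That a method will be scored faster than it is.** It can be, on verification. The same shift makes it look slower on intubation.
- **That rescue time is left out of verification time.** The rule is simply not stated. Group I's endpoint is defined by success, so a literal reading could keep the clock running until the tube is corrected.
- **That bronchial positioning in Groups I and II all falls after intubation.** The protocol's introduction describes rotating a conventional left tube while advancing it, so some positioning belongs to insertion there too. The documents do not say whether end-tidal CO₂ appears before or after bronchial entry in any group. For Group III, overlap of the two clocks is as plausible as a transfer of time between them.

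It can also be said that defining the start, the stop and a rescue rule for verification would be enough. That would settle the rescue question. It would not settle the other: with a common start at end-tidal CO₂, any Group III positioning done before that moment would still sit in the intubation clock.

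**Conclusion.** The point holds in a limited form. The plan has no common elapsed time to a verified tube, its verification endpoints differ by group, and its rule for rescue bronchoscopy is unstated. The separate comparisons can therefore credit time differently by method, and they cannot by themselves show which method gives a confirmed tube soonest. The illustrations show that a shift of 0.5 to 1.0 SD would produce a significant verification difference in about 50% to 99% of trials with no difference in the total. Those figures rest on assumed normal data, equal groups and assumed shifts, and the rescue figures on assumed rates and durations. A reader might also infer that the sample size is wrong. It is not shown to be: 93 reproduces, and power for a total cannot be derived because the outcome behind 0.33 is not named. This is an inexpensive improvement worth making, not a fatal fault.

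**What to change.** Record the clock time of final confirmed tube position before lateral positioning. Add to the protocol and SAP one elapsed-time outcome with the same definition in all groups: from first view of the vocal cords to the later of end-tidal CO₂ and final confirmed position, by whatever method was finally used, including any repositioning and rescue bronchoscopy.

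Define it as a single interval and not a sum of durations. Group II's verification is itself bronchoscopy, so a sum would count it twice, and Group III's clocks may overlap.

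Make this the lead time comparison. Keep intubation and verification times as tested secondary outcomes, so that the stated secondary purpose is still tested. State whether verification time includes rescue bronchoscopy.

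The cost is one extra recorded time, a sentence in the SAP, and possibly lower power for the total than for a single clock (step 4 of the working). The sponsor should say which outcome the 0.33 refers to and check power for the total once plausible SDs are available. The clock time has to be captured prospectively, since it may not be recoverable afterwards.
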